INSTRUCTIONS:

- *You may use a different format, order, outline or template provided the necessary information is included.*
- *Remove italicized instructions and subheadings prior to submission.*
- *Depending on the nature of what you are doing, some sections may not be applicable to your research. If so mark as “NA” or delete.*
- ***For any items described in the sponsor’s protocol, grant, contract, or other documents submitted with the application, include the appropriate text within this template.***
- *When you write a protocol, keep an electronic copy. You will need to modify this copy when making changes.*

1) Protocol Title

- a) The Effect of an Electronic Medical Record (EMR) Alert on Hepatitis B Screening: A Randomized Controlled Trial.
- b) May 15, 2019

2) Author of Protocol: [name] [name] (UC Davis Researcher)

3) IRB Review History: Not Applicable.

4) Objectives: The purpose of this study is to determine the effect of an EMR alert released through the UC Davis EMR on Hepatitis B screening.

5) Background

Chronic hepatitis B is a significant public health problem, which affects Asian American/Pacific Islander (API) Americans disproportionately. Of the CHB-positive foreign born persons living in the United States in 2009, 58% migrated from Asia (Kowdley et al. Hepatology 2012). Not only are foreign born APIs disproportionately infected with HBV, but they also have the highest incidence rates of hepatocellular carcinoma (HCC) and HCC-related mortality. According to analysis of the Surveillance Epidemiology and End Results (SEER) database, APIs had the highest age-adjusted HCC incidence rates consistently from 1992-2002. Hispanics had the second highest HCC incidence rates, but these were 40% lower than that of the APIs (El Serag et al. Arch Intern Med 2007). In the same study, APIs were also found to have the highest mortality associated with HCC of all groups studied with a relative risk of 3.6 compared to whites.

Despite this, the diagnosis of CHB remains low and only 20-30% of high risk individuals are aware of their infection (Cohen et al. J Viral Hepat 2011, Institute of Medicine, 2010). In 2014, the US Preventive Services Task Force placed a Grade B

PROTOCOL TITLE: The Effect of an Electronic Medical Record (EMR) Alert on Hepatitis B Screening: A Randomized Controlled Trial.

recommendation on screening for Hepatitis B particularly among persons born in countries and regions with high prevalence of HBV infection ($\geq 2\%$) or US born persons not vaccinated as infants whose parents were born in very high prevalence areas such as sub-Saharan Africa or central and Southeast Asia (LeFevre et al. Annals of Internal Medicine, 2014).

This study is part of a larger CDC-funded collaboration to increase screening and linkage to care for CHB (Sacramento Collaborative to Advance Testing and Care of Hepatitis B-SCrATCH B). Data from the Thousand Asian American Study at UC Davis suggests that the HBV prevalence in Sacramento County is 6%. Thus, we aim to increase HBV screening further with introduction of this EMR alert and to measure its effect in a randomized fashion.

6) Inclusion and Exclusion Criteria

Inclusion:

- Outpatients enrolled in the UC Davis EMR system aged 18 years and older with Chinese, Vietnamese, Japanese, Korean, or Indian surnames as determined by a peer reviewed listing of the 50 most common surnames within each ethnicity (Lauderdale et al. Population Research and Policy Review, 2000)
- Outpatients who have established in the UC Davis Primary Care Network
- No Hepatitis B surface Antigen (HBsAg) test previously
- No history of vaccination for HBV previously
- Primary care physicians (PCP) within the UCD network entities

Exclusion:

- Patients outside of this age range
- Pregnant patients
- Prisoners

7) Number of Subjects: We expect that 50% of intervention (EMR alert) patients will be tested for hepatitis B and that 20% in the control will be tested. Therefore, to achieve 80% power at the 0.05 significance level (2-sided), 45 patients in each group will be needed (90 total). While 90 is the minimum number of patients required to show a difference between control and EMR groups, the patient database has the potential to randomize 4,000 patients (2,000 patients in each arm). This could increase the validity of the alert. In addition, 10,000 more patients (5,000 in each arm) will be randomized to account patients with Medicare. In sum, 14,000 patients will be in the study. The inclusion of additional patients can help to increase the validity of such implementation. Physicians of the patients will be part of the study, in which they will be informed about the EMR alert study at the end. The number of PCPs involved in the study will be determined after the computer randomization of the study patients.

PROTOCOL TITLE: The Effect of an Electronic Medical Record (EMR) Alert on Hepatitis B Screening: A Randomized Controlled Trial.

8) Recruitment Methods

As mentioned, patients will be identified by EMR search based on their surname, previous HBsAg testing status, and previous HBV vaccination status. If they meet criteria for the study, the EMR alert will be released to their chart for their primary care provider to view. No in person recruitment will be done. PCPs will be informed at completion of the study about the EMR alert study. We will request for a HIPAA waiver of authorization as below:

HIPAA Authorization for Research (check all that apply):

Do you want to request a waiver of authorization?

Yes No

If you require a waiver of authorization, the IRB must make determinations to approve this waiver. Does the use or disclosure of PHI involve no more than a minimal risk to the privacy of the individual based on at least the presence of the following:

- I confirm that only authorized persons will be granted access to the identifiers; identifiers stored on a computers, electronic notebooks, mobile devices, data-storage devices will be encrypted and password protected; identifiers maintained in paper format will be kept in a locked area with access limited to only research staff who require access to conduct the study.
- I confirm that I will destroy the identifiers at the earliest opportunity consistent with the conduct of the research unless there is a health or research justification for retaining the identifiers or as otherwise required by law.

Date or event for when the identifiers will be destroyed: *October 31, 2024*

- I confirm that protected health information from this research will not be reused or disclosed to another person or entity, except as required by law, for authorized oversight of the research study, or other research for which the use or disclosure of PHI would be permitted.

Why will this waiver not adversely affect the privacy rights of the individual?

Identification of the subjects or their responses will not place them at risk of criminal or civil liability or be damaging to their financial standing, employability, insurability, reputation, or be stigmatizing, as appropriate protections will be implemented so that risks related to invasion of privacy and breach of confidentiality are no greater than minimal risk.

Why do you need this waiver to conduct this research?

PROTOCOL TITLE: The Effect of an Electronic Medical Record (EMR) Alert on Hepatitis B Screening: A Randomized Controlled Trial.

Patients will be identified as previously aforementioned. The only identifying information will be patient MRNs. There will be minimal risks for those identified who meet inclusion criteria. We will be activating the alert system-wide in a great number of patients. For these reasons, obtaining HIPAA authorization from subjects would not be feasible. Appropriate precautions will be taken to ensure that the privacy rights of those identified will be maintained.

9) Compensation to the Subjects

Patients will not be compensated.

10) Study Timelines

We anticipate that we will be able to recruit all 14,000 subjects for the study within 12 months. Once the EMR alert is released to a patient's chart, we will perform quarterly EMR data searches to determine if the primary care physician has ordered the HBsAg on those patients. Once a HBsAg test is ordered, the result will be recorded and the patient's participation in the study will end. If no HBsAg test is ordered, we will continue our quarterly EMR data searches to determine if the primary care physician orders the HBsAg at subsequent visits. The post-EMR release observation period may last up to 2 years. If no HBsAg test is ordered at the end of 2 year observation, the patient's participation in the study will end. The study will end on October 31, 2024 due to additional participants to allow time for data collection, analysis, and manuscript writing.

11) Study Endpoints

The study end points will be measurement of an HBsAg level after the EMR alert is release to each patients chart. As mentioned, certain proportion of patients will not reach this end point and this will be recorded.

12) Procedures Involved

- A list of patients meeting the eligibility requirements stated above will be obtained by searching the UC Davis EMR. At a given time, computerized 1:1 randomization of these patients will occur placing them in the intervention or control group. After randomization, the EMR alert will be released in the patients' charts notifying primary care doctors that these patients should be screened for hepatitis B with a HBsAg test. Control group patients will not have the EMR alert released in their chart and will undergo "usual care." As mentioned above (see Study Timelines), we will perform quarterly

PROTOCOL TITLE: The Effect of an Electronic Medical Record (EMR) Alert on Hepatitis B Screening: A Randomized Controlled Trial.

EMR searches to determine if a HBsAg test was ordered by the patient's primary care physician in response to the EMR alert. We will continue to perform quarterly EMR searches to determine if HBsAg tests are ordered at subsequent visits up to 2 years after the index visit.

- The data points that will be collected are MRN, age, sex, number of office visits, primary language, insurance type (private, medi-cal, or medicare), hepatitis B antigen test result, and date of the hepatitis B antigen test. All data points will strip off identifiable information. Study ID will be assigned and codes created are the only links to identifiable information.
- Patients who are randomly chosen for this study will be number coded. The only link to the patient identifiers will be through a separate key code which will be kept on a secure, password-protected computer. Any paper copies of such information will be kept in a locked filing cabinet in the division office accessible only to the PI and co-PI. The key code will be destroyed once it is confirmed that the data collection is complete.

13) Data and/or Specimen Management and Confidentiality

Will data be banked for future use?

Yes No

If yes, will the data that are banked be identifiable?

Yes, the data will be identifiable:
 No, the data will be completely anonymous.

No, the data will be stripped of identifiers and coded. The link to the individual's identity will not be accessible by the research team.

Where will the data be stored?

How long will the data be stored?

Who will have access to the data?

Describe the procedures to release data, including: the process to request a release, approvals required for release, who can obtain data or specimens, and the data to be provided with specimens.

PROTOCOL TITLE: The Effect of an Electronic Medical Record (EMR) Alert on Hepatitis B Screening: A Randomized Controlled Trial.

- 14) Data and/or Specimen Banking:** Not applicable.
- 15) Provisions to Monitor the Data to Ensure the Safety of Subjects:**
All data will be stored in a password protected Excel file on a secure server and uploaded to REDCap, which is a secure web application, used to build and manage online databases specifically for research, supported by the CTSC. Only those directly involved in research design, data gathering analysis will have access to the database.
- 16) Withdrawal of Subjects:** A patient will be withdrawn from the study by our staff if they fail to make at least one clinic appointment after release of EMR alert during the observation period. This may be due to change or insurance, being lost to follow up, or death.
- 17) Risks to Subjects**
This record/data review poses the risk of loss of confidentiality. This risk will be minimized by coding of patients' data and protection of private health information. This study will abide by all regulations in place governing the protection of human subjects and protected health information.
- 18) Potential Benefits to Subjects**
The direct benefit to subjects is that they may have an increased chance of screening for hepatitis B since the EMR alert will be reminding their primary care doctors to do so.
- 19) Vulnerable Populations:** Not applicable.
- 20) Multi-Site Research:** Not applicable.
- 21) Community-Based Participatory Research:** Not applicable.
- 22) Sharing of Results with Subjects**
The results will not be shared with the subjects.
- 23) Setting:** This project will be conducted solely among UC Davis primary care network clinic sites.
- 24) Resources Available**

[name], MPH is an Assistant Professor of Internal Medicine in the Division of Gastroenterology and Hepatology. He is primarily interested in

PROTOCOL TITLE: The Effect of an Electronic Medical Record (EMR) Alert on Hepatitis B Screening: A Randomized Controlled Trial.

outcomes research in viral hepatitis resulting in several first author publications in the field. Since coming to UC Davis, he has been involved in several projects including SCrATCH B and the R21 Biologic Basis of Disparities in Liver Cancer Survival Among Asian Americans Study. He will be the Principal Investigator of this Study and coordinate the randomization of subjects, EMR data searches, and statistical analysis.

[name] is a Professor, Division of Gastroenterology and Hepatology, Department of Internal Medicine, UC Davis School of Medicine and the Fellowship Director supervising the training of gastroenterologists and hepatologists at UC Davis. [name] serves as the primary hepatologist treating patients with hepatitis B in the UC Davis Health System. He is the Principle Investigator for SCrATCH B and the R21 Biologic Basis of Disparities in Liver Cancer Survival Among Asian Americans Study and will serve as a mentor to [name] during this study.

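### Patients no longer in care can be randomised, and the only rule that removes them is tied to alert release, which controls never have, so the effect may be diluted, unchanged or inflated.

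*Combined protocol and SAP*

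**What the plan says.** Section 6 (Inclusion and Exclusion Criteria) has one criterion that bears on being in care: "Outpatients who have established in the UC Davis Primary Care Network". It gives no look-back window, visit count or check that the patient is alive.

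Section 8 (Recruitment Methods) says that "patients will be identified by EMR search based on their surname, previous HBsAg testing status, and previous HBV vaccination status". None of the fields it names is a visit date. Section 12 (Procedures Involved) then randomises the resulting list 1:1 at a single time point, so entry is not triggered by a visit.

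Section 16 (Withdrawal of Subjects) takes patients out if "they fail to make at least one clinic appointment after release of EMR alert during the observation period". Of the reasons, it says: "This may be due to change or insurance, being lost to follow up, or death". Section 12 adds that "Control group patients will not have the EMR alert released in their chart".

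Sections 10 and 11 also define the observation period and the endpoint from alert release, while Section 12 counts the two years from an index visit. None of these sections gives a start date for controls, and none says whether withdrawn patients count in the denominator.

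Section 7 (Number of Subjects) states: "We expect that 50% of intervention (EMR alert) patients will be tested for hepatitis B and that 20% in the control will be tested". On total size it says: "In sum, 14,000 patients will be in the study".

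**The concern.** The alert is placed in the chart for the primary care provider to see, so it has little chance of acting on a patient who does not come back. Section 16 shows that the plan expects such patients and does not want them in the study. It identifies them only by attendance after randomisation, although the same EMR could screen on attendance beforehand.

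Two things are at stake. The first is the size of the absolute effect: patients who are never seen add to the denominator and almost nothing to the numerator. The second is the comparison itself. Followed literally, the withdrawal rule can be triggered only in the alert arm, because only that arm has an alert release. Removing non-attenders from one arm makes the arms differ even when the alert does nothing. The more inactive patients on the list, the larger either problem becomes.

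**Working it through.** **Inputs from the protocol.** Section 7: 50% tested with the alert, 20% without, two-sided 0.05, 80% power, 45 per arm as the minimum, 14,000 planned (7,000 per arm).

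**Assumptions.** The protocol gives no share of never-seen patients, so f = 10, 20, 30 and 40% is used. Never-seen patients are taken to have no test in either arm, f is the same in both arms, and 50% and 20% are taken to hold among patients seen.

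**1. The plan's own figure.** With a pooled rate of 0.35 and a difference of 0.30:

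n = [1.960·√(2·0.35·0.65) + 0.842·√(0.5·0.5 + 0.2·0.8)]² / 0.30² = 38.5 per arm.

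With continuity correction: n/4·[1 + √(1 + 4/(n·0.30))]² = 44.9, so 45 per arm. Section 7 is reproduced.

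**2. Three readings of what happens to never-seen patients.**

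- All kept: rates 0.5(1−f) and 0.2(1−f), difference 0.3(1−f), ratio 0.5/0.2 = 2.5.
- Removed equally from both arms: 0.5 and 0.2, difference 0.30.
- Removed from the alert arm only: 0.5 and 0.2(1−f), difference 0.3 + 0.2f.
- Removed from the alert arm only, alert with no effect: 0.2 and 0.2(1−f), spurious difference 0.2f.

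| f | All kept: rates | All kept: difference | Equal removal | Alert arm only | Alert arm only, no true effect |
|---|---|---|---|---|---|
| 10% | 45% v 18% | 27 points | 30 points | 32 points | 2 points |
| 20% | 40% v 16% | 24 points | 30 points | 34 points | 4 points |
| 30% | 35% v 14% | 21 points | 30 points | 36 points | 6 points |
| 40% | 30% v 12% | 18 points | 30 points | 38 points | 8 points |

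**3. Against sampling error.** With all kept at 7,000 per arm, the 95% half-width is 1.96·√[(p₁(1−p₁) + p₂(1−p₂))/7,000] = 1.47, 1.43, 1.38 and 1.32 points for f = 10 to 40%. The shift of 3 to 12 points is well outside that.

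For alert-arm-only removal with no true effect at f = 10%, the alert arm keeps 7,000·0.9 = 6,300 patients. The standard error is √(0.2·0.8/6,300 + 0.18·0.82/7,000) = 0.0068, so the half-width is 1.3 points. Even the smallest spurious difference, 2 points, exceeds it.

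**4. Power.** With all kept, the continuity-corrected minimum rises from 45 to 53, 62, 74 and 90 per arm. At 7,000 per arm power stays at about 100% throughout.

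**5. What a filter can achieve.** If a look-back filter catches a share s of future non-attenders, the share left is f(1−s)/[f(1−s) + 1−f]. With s = 80% (assumed):

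- f = 20%: 0.04/0.84 = 4.8% left; all-kept difference 0.3·0.952 = 28.6 points; spurious alert-arm-only difference 0.2·0.048 = 1.0 point instead of 4.
- f = 30%: 0.06/0.76 = 7.9% left; all-kept difference 27.6 points; spurious alert-arm-only difference 1.6 points instead of 6.

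The filter shrinks both problems and removes neither.

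**The case against.** The strongest reply is that Section 16 already deals with these patients. A reader might infer that the loose eligibility criterion necessarily shrinks the measured effect. The documents do not support that: shrinkage needs the never-seen patients to stay in the denominator, and this is left open. Removed equally from both arms, they leave the 30-point difference intact. Removed from the alert arm only, they push it upwards. This part of the objection stands. What it does not rescue is the rule itself, whose trigger has no control-arm counterpart.

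Second, a smaller difference among everyone established in the network is a valid estimate for the population that Section 6 names, and preferring current attenders is a choice of target. That also stands for the all-kept reading. But Section 16 shows that the plan has already chosen against non-attenders; it makes that choice after randomisation.

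Third, Section 7 does not say that its 50% and 20% refer to patients who are seen. If they already allow for non-attendance, there is no shortfall against expectation. That is correct, and it is why the figures are conditional.

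Fourth, the fields listed in Section 8 also omit age and pregnancy, so they are probably not the whole query, and the local meaning of being established is not given and might imply recent contact. This is fair, but no section states such a condition.

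Fifth, a look-back drops patients who return after a long gap, whom the alert could reach. That is a real cost.

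**Conclusion.** The point holds as a design weakness whose direction the documents leave unsettled. Eligibility sets no recent-attendance or vital-status condition, and the rule meant to deal with the consequence acts after randomisation on an event that occurs in one arm only. For an assumed never-seen share of 10–40%, no testing among those patients, and 50% and 20% among patients seen, the difference could be anywhere from 18 to 38 points depending on a denominator that is not stated. Under alert-arm-only withdrawal, 2 to 8 of those points would be spurious.

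Two stronger conclusions should be resisted. A reader might infer that the trial risks being underpowered: at 14,000 it does not, and with everyone kept the rate ratio stays at 2.5 (the odds ratio does fall, from 4.0 to 3.14 at 40%). A reader might also infer that an attendance filter would cure the problem. It cannot, because past visits do not identify patients who will die, leave or change insurance during the two years of observation. The filter is worth having only together with an analysis of everyone randomised and a common start date.

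**What to change.** 1. In Section 6, and in the EMR query of Sections 8 and 12, require before randomisation and identically for both arms that the patient is alive and has had at least one UC Davis primary care visit in a fixed look-back before the list date, for example 24 months. Choose the window from historical return rates in the EMR.
2. Replace the Section 16 withdrawal with a primary analysis of every randomised patient in the assigned arm, followed from the randomisation date in both arms. Align Sections 10, 11 and 12 with that date.
3. Report any analysis limited to patients with a visit as secondary, with the visit defined the same way and counted from the same date in both arms. The number of office visits is already among the data to be collected, but visit dates would be needed too.

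The cost is one more query condition and wording changes in these sections. The list may fall below 14,000, although at a never-seen share of 40% about 14,000·0.6 = 8,400 would remain if the filter removed exactly those patients, against a stated minimum of 90. The result would apply to patients in current care and would omit those who return after a long gap; the report should say so.

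### The endpoint is a measured HBsAg, but Section 10 ends follow-up at the order, so a test completed after a cancelled or unfilled first order could be missed (low priority)

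*Combined protocol and SAP*

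**What the plan says.** The outcome is a completed test. Section 11 states: "The study end points will be measurement of an HBsAg level". It adds that a "certain proportion of patients will not reach this end point and this will be recorded". Section 7 sizes the trial on the proportions tested, 50% with the alert and 20% without. The outcome fields in Section 12 are "hepatitis B antigen test result, and date of the hepatitis B antigen test"; neither an order date nor an order status is listed.

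Follow-up runs on a different event. The quarterly searches in Section 10 ask whether the primary care physician has placed an order. One sentence begins "Once a HBsAg test is ordered, the result will be recorded and the" and goes on to end the patient's participation. The next begins "If no HBsAg test is ordered, we will continue our quarterly EMR data searches". The exit at 2 years is also worded by order: "If no HBsAg test is ordered at the end of 2 year observation".

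Section 12 refers back to Section 10 and then says: "We will continue to perform quarterly EMR searches to determine if HBsAg tests are ordered at subsequent visits", for up to 2 years. It does not repeat the condition that no order has been placed. It also says of the link to identifiers: "The key code will be destroyed once it is confirmed that the data collection is complete".

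**The concern.** An order and a measurement are different events, and the plan stops looking at the first while counting the second. No section says what happens when an order is cancelled, or when the patient never has the blood drawn. If such a patient is tested later within the 2 years, that test meets Section 11, yet Section 10 requires no search that would find it. The patient would go into the analysis as not tested.

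This matters because it is the trial's only endpoint and the alert works by prompting orders. Orders without a result could therefore be more numerous in the alert arm. If the share of completed tests that is missed differed between arms, the estimated effect would be biased, and 14,000 patients would not remove that bias.

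**Working it through.** **1. The plan's own figure.** Inputs from Section 7: 50% against 20%, two-sided 0.05, 80% power. With pooled variance under the null, n0 = [1.96·√(2·0.35·0.65) + 0.8416·√(0.25 + 0.16)]² / 0.30² = 38.5. With the continuity correction, n = (n0/4)·[1 + √(1 + 4/(n0·0.30))]² = 44.9, which rounds up to 45 per group. The stated figure reproduces. It rests on proportions tested, which agrees with Section 11.

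**2. The follow-up rule applied to four kinds of patient.**

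- *Order found, result already available.* The result is recorded. No loss.
- *Order found, result pending.* Section 10 says the result will be recorded but names no time or search for doing so. The intent is clear; the step is missing.
- *Order never filled, no later test.* There is no measurement, so the patient correctly counts as not reaching the endpoint. No loss.
- *First order cancelled or unfilled, test completed later within 2 years.* There is no result to record when the order is found, and the Section 10 condition for further searches no longer holds. The later test is an endpoint that Section 10 does not look for. Section 12 might find it, through a new order at a later visit, if its unconditional wording governs.

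The firm gap is the fourth case. The second needs only a stated step.

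**3. What a loss would do, on assumed rates.** The documents give no completion rate and no time to result, so every loss rate here is an assumption. Take Section 7's rates as the true test rates and 7,000 per arm (2,000 + 5,000). Let m1 and m0 be the fractions of completed tests missed in the alert and control arms. The recorded difference in percentage points is

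50·(1 − m1) − 20·(1 − m0) = 30 − 50·m1 + 20·m0.

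| m1 | m0 | Recorded rates (%) | Difference (points) | Ratio |
|---|---|---|---|---|
| 2% | 2% | 49.0 / 19.6 | 29.4 | 2.50 |
| 10% | 10% | 45.0 / 18.0 | 27.0 | 2.50 |
| 10% | 5% | 45.0 / 19.0 | 26.0 | 2.37 |
| 4% | 10% | 48.0 / 18.0 | 30.0 | 2.67 |
| 2% | 10% | 49.0 / 18.0 | 31.0 | 2.72 |

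The difference shrinks when m1 > 0.4·m0 and grows when m1 < 0.4·m0, so even the direction depends on figures that the documents do not give.

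**4. Scale.** Ignoring clustering by physician, the 95% half-width at 7,000 per arm is 1.96·√(0.25/7,000 + 0.16/7,000) = 0.0150, or 1.5 points. A shift of that size needs a net 0.0150·7,000 = 105 more results missed in one arm than in the other, against about 3,500 expected in the alert arm and 1,400 in control. Power at 7,000 per arm stays near 100% even if 30% of results were missed in the alert arm alone (35% against 20%).

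**The case against.** The best reply is that the plan already intends to capture results. Section 10 says the result will be recorded and places that before participation ends. Section 12 collects the test result and its date, so a known order with a blank result would show as an outstanding item. Section 12 also restates the searches for up to 2 years without the condition. The key code is kept until data collection is confirmed complete, and Section 10 sets the study end at October 31, 2024 partly to leave time for data collection.

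Much of this stands. A reader might infer that results of pending orders are lost; the text does not support that, because it commits the team to recording them. A reader might also infer that missed results are lost for good once the key code is destroyed. That supposes completeness would be confirmed while ordered tests still lacked results, which the plan does not say.

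The case of a cancelled or unfilled first order remains. Recording the result of that order does not help when it never yields one. The wording in Section 12 helps only if it overrides Section 10, to which it refers back, and it too searches for orders. Keeping the key code makes a late result retrievable but obliges no one to look.

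**Conclusion.** The concern holds in a narrow form. Sections 10 and 12 conflict on whether searches continue after an order, and neither ties them to the measurement that Section 11 makes the endpoint. Under the literal Section 10, a patient tested within the 2 years after a cancelled or unfilled first order would be misclassified as not tested.

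It is tempting to go further and say that the alert's effect will be biased, or biased downward. The documents do not support that. More orders in the alert arm would mean more outstanding orders, but that does not show that a different fraction of completed tests is missed; with equal fractions the ratio stays at 2.5. The differences of 26.0 to 31.0 points in the table show sensitivity to assumed loss rates, not an expected effect. The 45 per group and the power are not in question. This is a low-priority inconsistency in how the endpoint is ascertained, not a demonstrated loss of endpoints.

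**What to change.** Reconcile Sections 10 and 12 so that both say the following, for both arms:

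- Quarterly searches continue until an HBsAg result is recorded or the existing 2-year window ends, whichever comes first. An order alone does not stop them.
- A patient counts as tested only if a result is dated within that window. An order without a result counts as not tested, in line with Section 11.
- Data collection is confirmed complete, and the key code destroyed, only after the last such search.

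The first rule also supplies the missing step for pending orders. The change is to wording only and needs no new data field; an order date could be added but is optional. The cost is that patients with an order but no result stay longer in searches that are already planned.
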